### 8.2.2. Reporting of Serious Adverse Events

All SAEs regardless of relationship to the study drug during the period starting from the time the patient signed the ICF through 7 days after the last study drug dose, will be

recorded in the eCRF. Once the Investigator becomes aware of an SAE, he/she must report the SAE to the Sponsor safety representative within 24 hours of knowledge of the event.

Safety Contact Information:

Pharmalex:

[contact]

[contact]

Email: [contact]

A written SAE report must include a full description of the event including the below parameters (include any protocol specific requirements):

- Diagnosis or description of event
- Onset date
- Severity assessment
- Causal relationship to the investigational product
- Assessment of seriousness of the event
- Corrective treatment administered for the SAE
- Action taken related to study drug include the following: dose interruption, dose delay, dose reduction, or study drug discontinuation
- Outcome of event and end date

Follow-up information for SAEs and information on non-serious AEs that become serious should also be reported to Sponsor Safety representative within 24 hours of receipt of follow-up information.

The Investigator must update the SAE form and submit any supporting documentation (eg, patient discharge summary or autopsy reports) to the ENYO safety designee via fax or email.

The Investigator is responsible for reporting all SAEs to the appropriate Institutional Review Board/Institutional Ethics Committee (IRB/IEC) in accordance with local laws and regulations. The Investigator is responsible for maintaining documentation in the study file that indicates the IRB/IEC has been properly notified.

### **8.2.3. Follow-up of Serious Adverse Events**

All events will be followed to resolution or stabilization or until 30 days after the patient completes the study. A final assessment of outcome will be made at that time.

### 8.3. Drug-Induced Liver Injury

#### 8.3.1. Normal values at baseline

Drug-induced liver injury (DILI) monitoring in patients with **normal liver transaminases and bilirubin at baseline** should be performed throughout the study according to the procedures summarized below:

- If patients with normal baseline liver indices develop elevations of aspartate aminotransferase (AST) or alanine aminotransferase (ALT) >2 upper limit of normal (ULN) or total bilirubin (TBL) >1.5 ULN values during the study, repeat testing should be performed within 48 hours.
- If there are persistent elevations (ALT or AST >2 ULN or TBL >1.5 ULN) upon repeat testing, close observation (testing and physical examination 2 to 3 times per week) should be implemented. An important purpose of the close observation is to gather additional clinical information to seek other possible causes of the observed liver test abnormalities, such as 1 of the following: acute viral hepatitis, alcoholic and autoimmune hepatitis, hepatobiliary disorders, cardiovascular causes, or concomitant treatments. Discontinuation of study drug should be considered.

[figure not shown]
Study drug should be discontinued, and the patient should be followed until resolution of signs or symptoms, in the following situations:

- ALT or AST >8 ULN.
- ALT or AST >5 ULN for more than 2 weeks.
- ALT or AST >3 ULN and (TBL >2 ULN or international normalized ratio [INR] >1.5).
- ALT or AST >3 ULN with the appearance of fatigue, nausea, vomiting, right upper quadrant pain or tenderness, fever, rash, and/or eosinophilia (>5%).

For any patients who present with a constellation of syndromes indicative of liver disease as per the Investigator's overall assessment (i.e., fatigue, nausea, vomiting, right upper quadrant pain or tenderness, fever, rash, and/or eosinophilia [>5%]), perform liver function tests to determine if liver disease is worsening.

Re-initiation of study drug may be considered after consultation with the Medical Monitor.

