#### 4.6. Stopping Rules

Dosing for a patient will be discontinued for any of the following events:

1. One occurrence of an SAE assessed to be definitely, probably or possibly related to dosing with the study drug.
2. One occurrence of a Grade 4 AE (i.e. life-threatening) assessed to be considered “possibly related” or “probably related” to the study drug
3. One occurrence a Grade 3 rash or higher or acute systemic allergic reaction.
4. Confirmation of any of the study drug discontinuation criteria as described in [Section 8.3](#).
5. Occurrence of any condition that, in the opinion of the Investigator, significantly jeopardizes the wellbeing and safety of the patient and is assessed to be probably related to dosing with the study drug.
6. Clinically significant changes in vital signs or ECGs (such as arrhythmias) assessed to be considered “possibly related” or “probably related” to the study drug (i.e., no alternative explanation likely).
7. Clinically significant changes in the safety laboratory tests assessed to be considered “probably related” to the study drug (i.e., no alternative explanation likely).
8. A subject experiences a breakthrough (defined by quantifiable HBV DNA increase of  $\geq 1 \log_{10}$  HBV DNA copies/mL above LLOQ) the subject should return to the study site for a confirmatory measurement within two weeks, and if virologic breakthrough is confirmed, EYP001a or placebo dosing should be stopped and NA treatment should be continued or modified at the investigator’s discretion.

If two or more patients meet study drug stopping criteria #1, or #3 to #8, recruitment and dosing should be suspended or terminated for the remaining patients, pending the outcome of a DSMC review. The DSMC must review all safety data and provide clearance prior to dosing any additional patients.

If one patient meets study drug stopping criteria #2, recruitment and dosing should be suspended or terminated for the remaining patients, pending the outcome of a DSMC review.

If one patient experiences a Grade 5 common terminology criteria for adverse event (CTCAE) toxicity (based on CTCAE, version 5.0), or if more than 2 patients develop a Grade 3 CTCAE toxicity in the same category, the study will be paused, and safety reports

will be submitted to the DSMC for review and clearance prior to dosing any additional patients.

In other situations, re-initiation of study drug may be considered after consultation with the Medical Monitor.

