### 8.3.2. Elevated values at baseline

Drug-induced liver injury (DILI) monitoring in patients with **elevations in liver transaminases or bilirubin at baseline** should be performed throughout the study according to the procedures summarized below:

- If patients with abnormal baseline liver indices develop elevations of AST or ALT  $>2$  baseline average or TBL  $>1.5$  baseline average values during the study, repeat testing should be performed within 48 hours.
- If there are persistent elevations (ALT or AST  $>2$  baseline average or TBL  $>1.5$  baseline average values) upon repeat testing, then close observation (testing and physical examination 2 to 3 times per week) should be implemented and discontinuation of study drug should be considered.

[figure not shown]
Study drug should be discontinued, and the patient should be followed until resolution of signs or symptoms, in the following situations:

- Baseline average measurements were  $<2 \times$  ULN and ALT or AST increases to  $>5 \times$  baseline measurements.
- ALT or AST increase  $>2 \times$  baseline average measurements AND the increase is accompanied by a concomitant increase in TBL to  $>2 \times$  baseline average measurements or the INR concomitantly increases by  $>0.2$ .

For any patients who present with a constellation of syndromes indicative of liver disease as per the Investigator's overall assessment (i.e., fatigue, nausea, vomiting, right upper quadrant pain or tenderness, fever, rash, and/or eosinophilia [ $>5\%$ ]), perform liver function tests to determine if liver disease is worsening.

Re-initiation of study drug may be considered after consultation with the Medical Monitor.

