### 8.3.3. General Considerations

For all patients, close observation for suspected drug-induced liver injury includes the following:

- Repeating liver enzyme (ALT, AST, and alkaline phosphatase) and serum bilirubin tests 2 or 3 times weekly.
- The frequency of repeat testing can decrease to once a week or less if abnormalities stabilize or the study drug has been discontinued and the patient is asymptomatic.
- Obtaining a more detailed history of symptoms and prior or concurrent diseases.
- Obtaining a history of concomitant drug use (including non-prescription medications and herbal and dietary supplement preparations), alcohol use, recreational drug use, and special diets.
- Ruling out acute viral hepatitis types A, B, C, D, and E; autoimmune or alcoholic hepatitis; non-alcoholic steatohepatitis; hypoxic/ischemic hepatopathy; and biliary tract disease.
- Obtaining a history of exposure to environmental chemical agents.
- Obtaining additional tests to evaluate liver function, as appropriate (e.g. INR, direct bilirubin).
- Considering gastroenterology or hepatology consultations.

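### After a combined transaminase plus bilirubin/INR stop, the protocol text allows restart on Medical Monitor consultation alone, and Section 4.6 is unclear against Section 8.3 on who may restart and when

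*Protocol*

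**What the plan says.** Section 8.3.1 (normal baseline) names four situations in which study drug should be discontinued. One is the combined pattern: "ALT or AST >3 ULN and (TBL >2 ULN or international normalized ratio [INR] >1.5". Section 8.3.2 (elevated baseline) names two. Its combined version is ALT or AST above twice the baseline average, with bilirubin above twice "baseline average measurements or the INR concomitantly increases by" more than 0.2. Both subsections require follow-up until signs or symptoms resolve. Both close with "Re-initiation of study drug may be considered after consultation with the Medical Monitor".

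Section 8.3.3 describes close observation for suspected drug-induced injury, including "Ruling out acute viral hepatitis types A, B, C, D, and E; autoimmune or alcoholic hepatitis".

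In Section 4.6 a confirmed 8.3 stop is criterion #4. The study-level rule is "If two or more patients meet study drug stopping criteria #1, or #3 to #8, recruitment and dosing should be suspended or terminated", pending DSMC review, and "The DSMC must review all safety data and provide clearance prior to dosing any additional patients". One patient is enough for criterion #2, a related Grade 4 event: "If one patient meets study drug stopping criteria #2, recruitment and dosing should be suspended or terminated for the remaining patients". One Grade 5 toxicity also pauses the study, as do more than two patients with Grade 3 toxicity in the same category. Section 4.6 then ends: "In other situations, re-initiation of study drug may be considered after consultation with the Medical Monitor". The synopsis repeats these rules.

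**The concern.** The combined criterion is the only 8.3.1 stop that adds a bilirubin or INR change to the transaminase rise. Its written route back to dosing is nevertheless the same single consultation that applies to an isolated ALT above 8 ULN. A site following the text could restart such a patient before the values have settled or before another cause has been found, and would not have departed from the protocol. The DSMC would not be called in because of that one patient.

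The balance favours caution. Section 1.5.2 says EYP001a has no proven clinical efficacy, and Section 5.7 lists increased hepatic enzymes among possible drug-related events. What is at stake is patient safety and consistent handling across sites. No power, alpha or estimation figure depends on this point.

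**Working it through.** The plan states no figure on this point, so the check sets the texts side by side.

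**Step 1: stops and restart routes (8.3.1, 8.3.2).**

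| Stop | Bilirubin/INR limb | Excepted from restart |
|---|---|---|
| 8.3.1: ALT/AST >8 ULN | no | no |
| 8.3.1: ALT/AST >5 ULN for over 2 weeks | no | no |
| 8.3.1: ALT/AST >3 ULN with TBL >2 ULN or INR >1.5 | yes | no |
| 8.3.1: ALT/AST >3 ULN with listed symptoms or eosinophilia | no | no |
| 8.3.2: baseline <2 ULN, ALT/AST >5 times baseline | no | no |
| 8.3.2: ALT/AST >2 times baseline with TBL >2 times baseline or INR rise >0.2 | yes | no |

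Stops: 4 + 2 = 6. Combined: 1 + 1 = 2. Excepted in the visible text: 0.

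**Step 2: is restart conditional on anything else?** Resolution appears as the end point of follow-up, and the search for other causes as part of close observation. Neither is linked to the restart sentence. Section 5.8 says 4.6 describes temporary and permanent stops, but 4.6 labels none as permanent. Stops for unblinding to the investigator (5.9) and for pregnancy (8.5) carry no restart sentence.

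**Step 3: DSMC trigger.** One combined case is one patient under #4, and 1 is below the required 2. Classing it as a related SAE (#1) or a probably related laboratory change (#7) leaves the threshold at two. Only a related Grade 4 event or a Grade 5 event lowers it to one, and the 8.3 thresholds require neither. Protocol 3.3 and SAP 16.1 use the same two-patient rule for unscheduled review. The two scheduled reviews are timed by how many patients have reached Week 8 and Week 12, not by a liver event.

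**Step 4: the restart sentence in 4.6 against 8.3.** Two readings are open.
- The opening words mean outside the DSMC-triggering situations just described. Medical Monitor-only restart is then closed during a suspension. A single combined case triggers no suspension, so the 8.3 route stays open for it.
- The opening words mean outside the listed individual stops. Section 4.6 then withholds the route for #4 while 8.3 grants it, and the two sections conflict.

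The clearance requirement speaks of additional patients and does not name those already stopped, so it does not settle the matter.

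**Step 5: how low can the 8.3.2 criterion fire?** Inclusion criterion 6c caps total bilirubin at 1.3 mg/dL. 1.3 / 2 = 0.65, so for a baseline average below 0.65 mg/dL the bilirubin limb can be met at a value still inside the entry limit. For INR, 1.5 - 0.2 = 1.3, so with a baseline INR below 1.3 the limb can be met below the absolute 1.5 used in 8.3.1. A rule for 8.3.2 should allow for this.

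**The case against.** The strongest reply is that safeguards already exist. Restart only may be considered and is not a right. Follow-up runs to resolution. The 8.3.3 work-up applies to all patients and would inform the Medical Monitor. SAEs reach the sponsor's safety representative within 24 hours, and stopping-rule listings go to both scheduled DSMC reviews. Figures 8 and 9 chart these same pathways, and the charter governs DSMC meetings, so either could hold a restart limit or single-case review. Section 5.4 reports no Hy's law case in EYP001-202. Section 1.4.3.3 reports that the five Grade 3 or 4 ALT/AST rises after 4 weeks in HBV subjects showed no dysfunction in bilirubin or INR. SAP Section 15 records enrolment suspended at about 25 randomizations.

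Much of this stands as a limit on size: the event is rare and unobserved in the cited data, and few further patients are exposed. It does not remove the gap. None of these safeguards is written as a condition for restart, and a limit found only in a figure or charter would sit beside unqualified body text.

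Two further objections stand in full. Protocol 3.1, 5.11 and Appendix A use study drug to include NA, so a bare prohibition on restarting study drug could be read as withholding NA, although Section 1.5.1 describes relapse and flares after NA is stopped. Demanding another cause in every 8.3.2 case would also become an absolute bar for unexplained low-value cases.

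A reader might infer that 4.6 lets a stopped patient restart during a suspension without DSMC clearance. The documents do not support that as a settled reading: dosing is suspended, and the opening words of the restart sentence can be taken to exclude it.

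**Conclusion.** The point holds as a specific, low-cost safety improvement. In the visible text, both combined stops (2 of 6) can be followed by restart on Medical Monitor consultation alone. Neither resolution nor an alternative cause is a stated condition, and one such patient does not by itself bring in the DSMC. Section 4.6 is ambiguous against 8.3 for listed stops and during a suspension.

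This rests on the body text only, with Figures 8 and 9 and the DSMC charter unseen. No event rate is claimed and no combined case is reported in the cited earlier data, so the text does not show an observed hazard. Nor does it support a blanket ban on restart, given how low the 8.3.2 criterion can fire. Routine DSMC clearance for each patient outside a suspension would be a debatable addition and is not needed to close the gap.

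**What to change.** Replace the closing sentence of 8.3.1 with text to this effect:

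> After ALT or AST >3 ULN with TBL >2 ULN or INR >1.5, EYP001a/placebo must not be restarted unless the 8.3.3 work-up documents another cause and the values have resolved, in consultation with the Medical Monitor. NA is continued or modified at the investigator's discretion. After any other 8.3 stop, restart of EYP001a/placebo remains open once the Medical Monitor has been consulted.

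Use the same text in 8.3.2 for its combined criterion, with one change. Apply the other-cause requirement only when bilirubin or INR also passes an absolute limit, for example TBL >2 ULN or INR >1.5. Below that, require resolution plus Medical Monitor consultation.

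In 4.6 and the synopsis, state that during a DSMC suspension no patient, including one already stopped, restarts EYP001a/placebo without DSMC clearance, and that restart otherwise follows Section 8.3. Align Figures 8 and 9 if they differ.

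This is a text change by amendment or clarification letter, with no new visits, samples or sample size, because the work-up and the DSMC already exist. The price is that a few patients may stay off EYP001a/placebo longer or permanently.

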**Figure 8      Normal liver transaminase and bilirubin at baseline**

ALT: alanine aminotransferase; AST: aspartate aminotransferase; INR: international normalized ratio; TBL: total bilirubin; ULN: upper limit of normal.

### 8.3.2. Elevated values at baseline

Drug-induced liver injury (DILI) monitoring in patients with **elevations in liver transaminases or bilirubin at baseline** should be performed throughout the study according to the procedures summarized below:

- If patients with abnormal baseline liver indices develop elevations of AST or ALT  $>2$  baseline average or TBL  $>1.5$  baseline average values during the study, repeat testing should be performed within 48 hours.
- If there are persistent elevations (ALT or AST  $>2$  baseline average or TBL  $>1.5$  baseline average values) upon repeat testing, then close observation (testing and physical examination 2 to 3 times per week) should be implemented and discontinuation of study drug should be considered.

[figure not shown]
Study drug should be discontinued, and the patient should be followed until resolution of signs or symptoms, in the following situations:

- Baseline average measurements were  $<2 \times$  ULN and ALT or AST increases to  $>5 \times$  baseline measurements.
- ALT or AST increase  $>2 \times$  baseline average measurements AND the increase is accompanied by a concomitant increase in TBL to  $>2 \times$  baseline average measurements or the INR concomitantly increases by  $>0.2$ .

For any patients who present with a constellation of syndromes indicative of liver disease as per the Investigator's overall assessment (i.e., fatigue, nausea, vomiting, right upper quadrant pain or tenderness, fever, rash, and/or eosinophilia [ $>5\%$ ]), perform liver function tests to determine if liver disease is worsening.

Re-initiation of study drug may be considered after consultation with the Medical Monitor.

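### The Section 8.3.2 stop list, used when any baseline transaminase or bilirubin is raised, lacks two mandatory stops that Section 8.3.1 gives patients with normal baselines

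*Protocol*

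**What the plan says.** Protocol Section 8.3.1 covers patients whose baseline transaminases and bilirubin are all normal. Section 8.3.2 covers those with "elevations in liver transaminases or bilirubin at baseline". The two groups are complementary, so one raised test moves the patient to 8.3.2 for everything.

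Section 8.3.1 lists four discontinuation criteria:
- "ALT or AST >8 ULN";
- "ALT or AST >5 ULN for more than 2 weeks";
- ALT or AST above 3 x ULN together with total bilirubin (TBL) above 2 x ULN or INR above 1.5;
- "ALT or AST >3 ULN with the appearance of fatigue, nausea, vomiting, right upper quadrant pain or tenderness, fever, rash, and/or eosinophilia" (above 5%).

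Section 8.3.2 lists two, both set against the patient's own baseline:
- ALT or AST above 5 x baseline, if the baseline average was below 2 x ULN;
- ALT or AST above 2 x baseline average, with TBL above 2 x baseline average or an INR rise above 0.2.

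For symptoms, the 8.3.2 text asks the site to "perform liver function tests to determine if liver disease is worsening". For a persistent rise above 2 x baseline it asks for close observation and for discontinuation to be considered.

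Section 4.6 rule 4 makes the Section 8.3 criteria binding: dosing ends on "Confirmation of any of the study drug discontinuation criteria as described in" that section, with no causality judgement. Rules 5 and 7 can also end dosing, but only if the event is judged probably related; rule 5 requires that it "is assessed to be probably related to dosing with the study drug".

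**The concern.** Symptoms alongside a raised transaminase, and a large rise that does not settle, are two of the situations in which Section 8.3.1 takes the decision out of the investigator's hands. The 8.3.2 text leaves both to judgement, and it does so for patients who start with raised liver tests.

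The plan expects such patients. Inclusion criterion 6a admits ALT and AST up to 2 x ULN, and exclusion criterion 8 has a separate elastography limit for baseline ALT above ULN.

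Rules 5 and 7 of Section 4.6 do not reliably fill the gap for a non-serious event. Both need a probable relationship to study drug, and rule 7 adds that no other explanation is likely. Section 1.4.3.3 records that earlier Grade 3 and 4 rises were read as flares of the underlying hepatitis B. An investigator who takes the same view would not reach that threshold.

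**Working it through.** The plan states no figure here to reproduce. The check applies both sets of text criteria to the same patient. Let b be baseline ALT in multiples of ULN; AST works the same way.

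**Limits from the text**
- 8.3.2, enzyme alone: stop above 5 x b.
- 8.3.2, combined: stop above 2 x b, but only with TBL above 2 x baseline or an INR rise above 0.2.
- 8.3.1, symptoms: stop above 3 x ULN.
- 8.3.1, sustained: stop above 5 x ULN for more than two weeks.

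**No qualifying TBL or INR change (all values x ULN)**

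| Baseline b | 8.3.2 enzyme-alone limit, 5 x b | Proposed symptom limit, larger of 3 and 2 x b | Symptomatic ALT with no mandatory 8.3 stop | ALT lasting over 2 weeks with no mandatory 8.3 stop |
|---|---|---|---|---|
| 1.2 | 6.0 | 3.0 (2 x b = 2.4) | above 3.0, up to 6.0 | above 5, up to 6.0 |
| 1.5 | 7.5 | 3.0 (2 x b = 3.0) | above 3.0, up to 7.5 | above 5, up to 7.5 |
| 1.9 | 9.5 | 3.8 (2 x b = 3.8) | above 3.8, up to 9.5 | above 5, up to 9.5 |

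The fourth column starts at the larger of 3 x ULN and 2 x baseline. A patient who starts at 1.9 should not have to stop for a rise to 3.1, which is only 3.1 / 1.9 = 1.6 times baseline. Against the bare 8.3.1 limit, the gap at 1.9 would start at 3.0.

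**Worked patient.** Baseline ALT is 1.2, and the patient has symptoms with ALT at 5 x ULN. The rise is 5 / 1.2 = 4.2 times baseline, below the five-fold limit. It exceeds 2 x 1.2 = 2.4, so retesting within 48 hours follows and, if it persists, close observation with discontinuation considered. The text requires no stop. Had all baseline tests been normal, the stop would apply above 3 x ULN.

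**Where the gap begins.** The symptom gap exists when 5 x b exceeds 3, that is b above 0.6. The sustained-rise gap exists when 5 x b exceeds 5, that is b above 1.0.

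**Does the sustained stop need a baseline guard?** No. At the highest admissible baseline of 2.0, 5 x ULN is already 5 / 2.0 = 2.5 times baseline. The 8.3.2 retesting trigger is at most 2 x 2.0 = 4 x ULN, so anyone above 5 x ULN is already being retested.

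**Frequency.** The documents do not give it. Section 1.4.3.3 reports five Grade 3 or 4 ALT/AST rises among CHB subjects (Section 1.4.3 counts four), and Section 5.4 reports two Grade 3 cases in a NASH study with 24 enrolled. The CHB study was mostly in untreated patients, whereas this trial requires suppressed HBV DNA on at least 12 months of therapy. Those cases were also described as without signs of liver dysfunction, or as isolated and transient. They give no rate for the events at issue here.

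**The case against.** **Figure 9 is not shown.** It is the flowchart for 8.3.2 and may carry criteria that the text lacks. This stands as a limit on the finding. But the text list reads as complete, so a figure with extra stops would itself have to be reconciled with the text.

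**The patient is not left unprotected.** Retesting, close observation and considered discontinuation apply. Rule 1 of Section 4.6 stops dosing for a serious event judged only possibly related. Section 4.7 lets the investigator discontinue a participant at any time, for an adverse event or any other reason, with no causality test. All of this stands. A reader might infer that these patients go unmonitored or cannot be stopped, and the documents do not support that. The difference is between a discretionary and an automatic stop.

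**Own-baseline limits are a legitimate choice.** A reader might also infer that 8.3.2 is wrong to apply own-baseline multiples to a test that was normal at baseline, since a patient with raised bilirubin and ALT 0.5 x ULN must stop above 5 x 0.5 = 2.5 x ULN, against 8 under 8.3.1. The documents do not make this an error. Stopping at a five-fold rise is cautious, and 8.3.2 allows re-initiation after consultation with the Medical Monitor. Judging each test by its own baseline status would let that ALT reach 8 x ULN, a 16-fold rise (8 / 0.5), while a raised AST of 1.2 still stopped at 6.0.

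**Timing.** SAP Section 15 records that enrolment was suspended on 17 February 2021, after about 25 randomizations. A change would therefore reach few remaining weeks of dosing unless enrolment restarts. This limits the benefit but does not alter the reading of the text.

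**Conclusion.** The point holds for the two omitted stops. For baseline ALT of 1.2, 1.5 or 1.9 x ULN, the 8.3.2 text requires no stop for symptomatic ALT from above 3 x ULN (3.8 at baseline 1.9 with the baseline guard) up to 6.0, 7.5 or 9.5 x ULN. Nor does it require one for ALT from above 5 x ULN up to those values lasting more than two weeks. Patients with normal baselines must stop in both cases.

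This assumes that TBL does not exceed 2 x baseline, that INR does not rise by more than 0.2, and that Figure 9 adds nothing. Few patients are likely to be affected, and no frequency can be derived from the documents. Label: cheap improvement.

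**What to change.** Add two criteria to the 8.3.2 discontinuation list:
- ALT or AST >3 x ULN and >2 x baseline average, with the symptoms listed in 8.3.1;
- ALT or AST >5 x ULN for more than 2 weeks.

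Make Figure 9 agree with the amended text. Keep the existing own-baseline limits for all tests and do not relax them test by test.

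Optionally, say in 8.3 that the baseline average is the screening and Day 1 pre-dose mean already defined in SAP Section 3.2 for ALT, AST and TBL. At present 8.3 gives no cross-reference, and Protocol Section 11.1 defines baseline as the last pre-dose value.

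The cost is a short amendment. Section 12.1 allows a change that reduces risk to start before IRB/IEC approval, provided the committee is informed in writing and approval follows. No new samples are needed, because liver tests and adverse event checks are already scheduled fortnightly on treatment. The downside is possibly a few more mandatory stops. Each would count under rule 4 of Section 4.6, where two patients are enough to suspend recruitment and dosing pending DSMC review.
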